6.2.1 PAC-1 Dose Reduction

Dose Reduction ^{a,b,c}	Dose	Dose
Starting Dose	750 mg daily	625 mg daily
First Dose Reduction	625 mg daily	500 mg daily
Second Dose Reduction	500 mg daily	375 mg daily
Third Dose Reduction	375 mg daily	250 mg daily
Fourth Dose Reduction	250 mg daily	NA

^a In the event a dose modification is needed, initiation of re-treatment should be delayed 1 to 2 weeks to allow for recovery from treatment-related toxicity

^b If the patient has not recovered after a 2-week delay, discontinue treatment

^c Up to four dose reductions are allowed if the starting dose is 750 mg. If subsequent cycles require additional dose reductions, treatment will be discontinued.

6.3 Dose Modifications for Entrectinib Toxicity

Dose Modifications for Entrectinib-Related Adverse Events

Toxicity*	Grade 1	Grade 2	Grade 3	Grade 4
Non-hematologic	Continue at same dose level	Continue at same dose level	Withhold dose until toxicity is \leq G1 or has returned to baseline, then reduce by 1 dose level and resume treatment	Withhold dose until toxicity is \leq G1 or has returned to baseline, then reduce by 1 dose level and resume treatment; or discontinue treatment as per the Investigator's discretion
Central Nervous System Effects	Continue at same dose level	Intolerable Grade 2; Withhold dose until recovery to \leq Grade 1 or to baseline. Resume at same dose or reduced dose, as clinically appropriate.	Withhold dose until recovery to \leq Grade 1 or to baseline. Resume at same dose or reduced dose, as clinically appropriate.	Discontinue treatment permanently

Hematologic	Continue at same dose level	Continue at same dose level	Withhold dose until toxicity is \leq G2, or has returned to baseline, then resume treatment at the same dose level or reduce by 1 dose level as per the Investigator's discretion Grade 3 lymphopenia without other dose-limiting events (e.g., opportunistic infection) may continue study treatment without interruption	Withhold dose until toxicity is \leq G2, or has returned to baseline, then reduce the dose by 1 dose level and resume treatment Grade 4 lymphopenia without other dose-limiting events (e.g., opportunistic infection) may continue study treatment without interruption
QT Interval Prolongation	QTc greater than 500 ms		Withhold entrectinib until QTc interval recovers to baseline. Resume at same dose if factors that cause QT prolongation are identified and corrected. Resume at reduced dose if other factors that cause QT prolongation are not identified.	
			Permanently discontinue entrectinib	
Vision Disorders	Grade 2 or above		Withhold entrectinib until improvement or stabilization. Resume at same dose or reduced dose, as clinically appropriate.	
Anemia or neutropenia	Grade 3 or 4		Withhold entrectinib until recovery to less than or equal to Grade 2. Resume at the same dose or reduced dose, as clinically appropriate.	
Congestive heart failure	Continue at same dose level	Withhold dose until toxicity is \leq G1 or has returned to baseline, then reduce by 1 dose level and resume treatment	Withhold dose until toxicity is \leq G1 or has returned to baseline, then reduce by 1 dose level and resume treatment	Discontinue treatment permanently

Pneumonitis (in absence of disease progression, pulmonary embolism, positive cultures or radiation effect)	Withhold dose until toxicity is Grade 0, then resume treatment at same dose Discontinue treatment permanently if pneumonitis recurs	Withhold dose until toxicity is Grade 0, then resume treatment at same dose Discontinue treatment permanently if pneumonitis recurs	Discontinue treatment permanently	Discontinue treatment permanently
Hyperuricemia symptomatic or Grade 4	
Initiate urate-lowering medication.
 
 Withhold entrectinib until improvement of signs or symptoms. Resume entrectinib at same or reduced dose. 			
Hepatotoxicity	Continue at same dose level	Continue at same dose level	
Withhold dose until recovery to \leq Grade 1 or to baseline.
 
Resume at same dose if resolution occurs within 4 weeks.
 
Permanently discontinue if adverse reaction does not resolve within 4 weeks.
 
Resume at a reduced dose for recurrent Grade 3 events that resolve within 4 weeks.
	
Withhold dose until recovery to \leq Grade 1 or to baseline.
 
Resume at same dose if resolution occurs within 4 weeks.
 
Permanently discontinue if adverse reaction does not resolve within 4 weeks.
 
Permanently discontinue for recurrent Grade 4 events

	ALT or AST greater than 3 times ULN with concurrent total bilirubin greater than 1.5 times ULN (in the absence of cholestasis or hemolysis) permanently discontinue treatment.			
Other Clinically Relevant Adverse Reactions	Grade 3 or 4		
Withhold entrectinib until adverse reaction resolves or improves to recovery or improvement to Grade 1 or baseline.
 
Resume at the same or reduced dose, if resolution occurs within 4 weeks.
 
Permanently discontinue if adverse reaction does not resolve within 4 weeks.
 
Permanently discontinue for recurrent Grade 4 events.
	

*dose modifications to be based on worst toxicity grade as per NCI CTCAE v5.0

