6.2 Dose Modifications for PAC-1 Toxicity

CTCAE v 5 Adverse Effects Terms & Descriptions)	PAC-1 Dose Modifications
Any other grade 3 non-hematologic toxicity	Hold dose until improvement to grade ≤ 1 then decrease dose by one dose level below level that caused toxicity.
Grade ≥ 2 neurologic toxicity detected at any time while on study treatment	Hold dose until improvement to grade ≤ 1 then decrease dose by one dose level below level that caused toxicity.
Any grade cerebrovascular ischemia or hemorrhage	Discontinue treatment.
Any other grade 4 non-hematologic toxicity	Discontinue treatment.
Neutrophils < 500 cells/mm 3	Hold dose until improvement to grade ≤ 1 then decrease dose by one dose level below level that caused toxicity.
Febrile Neutropenia	Hold dose until improvement to grade ≤ 1 then decrease dose by one dose level below level that caused toxicity.
Platelets $< 25,000/\text{mm}^3$ or platelets $< 50,000/\text{mm}^3$ with bleeding	Hold dose until improvement to grade ≤ 1 then decrease dose by one dose level below level that caused toxicity.
Any other grade 3 hematologic toxicity	Hold dose until improvement to grade ≤ 1 then decrease dose by one dose level below level that caused toxicity.
Any other grade 4 hematologic toxicity	Discontinue treatment.

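### In the Section 6.3 entrectinib table, two pairs of overlapping rows give different actions for the same event, and no rule says which row governs

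*Combined protocol and SAP*

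**What the plan says.** Section 6.3 lists actions for entrectinib-related events by row and grade. The relevant cells are:

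- *Hematologic*, Grade 4: hold until Grade 2 or lower, or baseline, "then reduce the dose by 1 dose level and resume treatment".
- *Anemia or neutropenia*, Grade 3 or 4: hold until Grade 2 or lower, and then "Resume at the same dose or reduced dose, as clinically appropriate".
- *Non-hematologic*, Grade 3: hold until Grade 1 or lower, or baseline, "then reduce by 1 dose level and resume treatment". The cell gives no time limit.
- *Other Clinically Relevant Adverse Reactions*, Grade 3 or 4: "Resume at the same or reduced dose, if resolution occurs within 4 weeks", and "Permanently discontinue if adverse reaction does not resolve within 4 weeks".
- *Hematologic*, Grade 4, lymphopenia exception: "Grade 4 lymphopenia without other dose-limiting events (e.g., opportunistic infection) may continue study treatment without interruption".

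The table's only footnote tells the reader to use the worst CTCAE grade. Section 6.3.2 gives the ladder 600, 400, 200 mg and allows two reductions; needing a further one means stopping. Its footnote b stops treatment if the patient has not recovered after a 2-week delay. Sections 6.1 and 6.4 stop treatment on delays of about 4 weeks, counted at the start of a cycle. In Section 6.2, the PAC-1 table has a row for "Any other grade 4 hematologic toxicity" whose action is to discontinue, with no lymphopenia exception.

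**The concern.** Two sites can follow the same table, treat the same event differently, and both be compliant. Neither action could clearly be called a deviation.

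More is at stake than one dose step. A compulsory reduction spends one of two permitted reductions, while resuming at the same dose spends none, so the choice of row also affects who later reaches the end of the ladder and leaves treatment. For a slow recovery, the choice can decide at once whether treatment continues. In a single-arm Phase 2 of 35 subjects, dose intensity and discontinuations then depend partly on how a site reads the table.

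**Working it through.** The plan states no figure on this point, so the check is a comparison of the text, with arithmetic only on the dose ladder and the time limits.

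**1. Grade 4 anemia or neutropenia.** Both rows apply and both hold to Grade 2 or lower. They differ on resumption:

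| Row | First event, from 600 mg | Reductions spent |
|---|---|---|
| Hematologic | 400 mg, compulsory | 1 of 2 |
| Anemia or neutropenia | 600 or 400 mg | 0 or 1 of 2 |

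At Grade 3 there is no conflict, because the Hematologic row also leaves the dose to the investigator.

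**2. Grade 3 non-hematologic event with no dedicated row.** Non-hematologic and Other Clinically Relevant Adverse Reactions are both residual categories. By time to recovery, from 600 mg:

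| Recovery at | Non-hematologic row | Other row | Footnote b of 6.3.2, if it applies |
|---|---|---|---|
| 1 week | 400 mg | 600 or 400 mg | no stop |
| 3 weeks | 400 mg | 600 or 400 mg | stop (3 > 2 weeks) |
| 5 weeks | 400 mg | permanent stop (5 > 4 weeks) | stop |

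The 3-week line yields three possible outcomes: 600 mg, 400 mg or discontinuation.

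**3. Do the cycle-start limits settle it?** No, because they run on a different clock. As an illustration, assume a hold that begins on Cycle 1 Day 15 and lasts 5 weeks. It ends on day 15 + 35 = 50. Cycle 2 was due on day 29, so the delay to the cycle is 50 − 29 = 21 days, or 3 weeks. That is inside the 4-week limits of Sections 6.1 and 6.4, yet the event lasted 35 days, which is beyond the 28 days of the Other row.

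**4. Size of the step.** First reduction: (600 − 400)/600 = 33%. Second: (400 − 200)/400 = 50%. With three successive Grade 3 events of this kind, each recovering within 2 weeks, the compulsory row gives 600 → 400 → 200 → stop. The discretionary row permits 600 mg throughout.

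**5. Search for a precedence rule.** The footnote to the Section 6.3 table selects a grade, not a row. The residual wording in the PAC-1 table orders rows only within that table. Section 11.2.4 has relatedness judged for each drug but does not address row choice. Sections 5.1.2, 6.1 and 6.4 give no precedence rule either.

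**6. Lymphopenia.** If study treatment in the exception means entrectinib alone, the two tables can both be followed: entrectinib continues and PAC-1 stops. If it includes PAC-1, they contradict each other. The text does not say which is meant.

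**The case against.** The best defence has four parts.

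*A named row naturally overrides a general one.* This would resolve anemia and neutropenia, but the convention is not written. It cannot separate two catch-all rows, so the Grade 3 non-hematologic overlap remains.

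*A site that reduces by one level satisfies both rows.* This is true for anemia and neutropenia, and for a non-hematologic event that recovers within 2 weeks. There the conflict is between compulsory and optional reduction, not between incompatible acts. It fails for slower recoveries: between 2 and 4 weeks footnote b and the Other row part ways, and after 4 weeks one row resumes while the other stops permanently.

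*A 4-week limit already exists in Sections 6.1 and 6.4.* This stands in part: the limit is not unique to the Other row. But those sections count from the planned cycle start and do not cover every mid-cycle hold.

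*The tables grant discretion on purpose.* They do, and some variation between sites would remain even with a clear rule. That does not explain why one row removes discretion that another row grants for the same event.

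A reader might also infer that Grade 4 lymphopenia is a third conflict of equal weight. The documents do not support that. The two instructions sit in tables for different drugs, the PAC-1 action column is headed for PAC-1, and relatedness is assessed drug by drug. Only the ambiguous term, and the absence of a rule for an event attributed to both drugs, remain.

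**Conclusion.** The point holds and the text is wrong as written: two row overlaps within the Section 6.3 table, with no stated precedence. The Grade 3 non-hematologic pair is the clearer, because no ordinary reading convention resolves it. The lymphopenia wording is secondary.

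The consequence for an affected subject is one reduction step (33% or 50%, depending on the current dose), use of one of two permitted reductions and, for recoveries beyond 2 weeks, possibly discontinuation.

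Two wider readings are not supported. One is that every Grade 4 hematologic and every Grade 3 non-hematologic event is affected. The table covers entrectinib-related events, several toxicities have their own rows, and the lymphopenia exception applies only without other dose-limiting events. The other is that 3-month PFS or the safety results are materially distorted. The documents give no event rates, so the number of subjects affected is unknown and the effect cannot be sized. Sample size and type I error do not depend on this issue.

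The conclusion assumes that no governing rule exists outside the documents, for example in site instructions.

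**What to change.** Reconcile the rows of Section 6.3 with one another and with Section 6.3.2:

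- For Grade 4 anemia or neutropenia, and for Grade 3 non-hematologic events without a dedicated row, either remove the overlap or add a sentence stating which row governs.
- State how the 2-week limit in footnote b of Section 6.3.2, the 4-week limit in the Other Clinically Relevant Adverse Reactions row, and the cycle-start limits in Sections 6.1 and 6.4 fit together, including the date from which each is counted.
- State whether study treatment in the lymphopenia text means entrectinib only. If it includes PAC-1, reconcile it with the Section 6.2 table.

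The clinical team must choose the actions; this review does not favour any of them. The cost is a table edit or a short precedence statement, issued as a protocol amendment and passed to the sites. The design, sample size and analysis do not change.

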6.3.2 Entrectinib Dose Reduction

Dose Reduction ^{a,b,c}	Dose
Starting Dose	600 mg daily
First Dose Reduction	400 mg daily
Second Dose Reduction	200 mg daily

^a In the event a dose modification is needed, initiation of re-treatment should be delayed 1 to 2 weeks to allow for recovery from treatment-related toxicity

^b If the patient has not recovered after a 2-week delay, discontinue treatment

^c Two dose reductions are allowed. If subsequent cycles require additional dose reductions, treatment will be discontinued.

6.4 Protocol Therapy Discontinuation

In addition to discontinuation from therapy related to toxicities as outlined above, a subject will also be discontinued from protocol therapy and followed per protocol under the following circumstances outlined below. The reason for discontinuation of protocol therapy will be documented on the electronic case report form (eCRF)

- If there is evidence of disease progression
- If the treating physician thinks a change of therapy would be in the best interest of the subject
- If the subject requests to discontinue protocol therapy
- If the protocol therapy exhibits unacceptable toxicity
- If a female subject becomes pregnant
- If there is a ≥ 4 week delay between cycles due to a treatment related adverse event.
- Subjects can stop study participation at any time. However, if they decide to stop, subjects will continue to be followed as per Section 7 calendar

6.5 Protocol Discontinuation

If a subject decides to discontinue from the protocol (and not just from protocol therapy) all efforts should be made to complete and report study assessments as thoroughly as possible. A complete final evaluation at the time of the subject's protocol withdrawal should be made with an explanation of why the subject is withdrawing from the protocol. If the reason for removal of a subject from the study is an adverse event, it will be recorded on the eCRF.

7 STUDY CALENDAR & EVALUATIONS

Study Evaluation Cycle = 28 days	Screening	Cycle 1	Cycle 2 and Subsequent	Safety follow up visit ¹²	Long-term Follow up ¹³
	-28 days	Day 1 ± 3 days	Day 1 ± 3 days	30 days post last dose	Every 2-3 months
REQUIRED ASSESSMENTS					
Informed Consent	X				
Medical History ¹	X				
Diagnosis and Disease Staging ¹	X				
Physical Exam ²	X	X	X	X	
Vital signs and ECOG Performance Status ²	X	X	X	X	
ECG ³	X	X ³	X ³	X	
ECHO ³	X				
Mini Mental Status Exam (MMSE) and Neurologic exam ⁴	X	X	X ⁴	X ⁴	
AEs & concomitant medications	X	X	X	X	
LABORATORY ASSESSMENTS					
Complete Blood Cell Count with diff (CBC)	X	X ¹¹	X	X	
Comprehensive Metabolic Profile (CMP) ⁵	X	X ¹¹	X	X	
Ammonia, Lactate Dehydrogenase and Uric Acid ⁵	X	X ¹¹	X		
PT/INR and aPTT ⁵	X				
Pregnancy test (serum or urine) (WOCBP) ⁵	X	X ⁵			
Urinalysis ⁵	X				
DISEASE ASSESSMENT					
CT of chest ⁶	X		X ⁶		X ⁶
CT or MRI of abdomen and pelvis ⁶	X		X ⁶		X ⁶
MRI Brain ⁶	X ⁶				
TREATMENT EXPOSURE					
PAC-1 ⁷		X ⁷	X ⁷		
Entrectinib ⁷		X ⁷	X ⁷		
SPECIMEN COLLECTION					
Plasma for PAC-1 PK/PD ⁸		X ⁸			
Plasma for Entrectinib PK/PD ⁸		X ⁸			
Blood sample for somatic baseline ⁹		X ⁹			
Blood samples for CTCs, MOA and ctDNA ⁹		X ⁹	C2D1	X ⁹	
Archival or Fresh Tumor Tissue ¹⁰	X ¹⁰	X ¹⁰			
FOLLOW-UP					
Survival Status, Subsequent Therapy					X

Key to Footnotes

1: Medical History including all prior anti-cancer treatment. Other data to be obtained during this assessment includes a smoking history questionnaire and trial awareness question. Diagnosis and staging to include pathology report and TNM staging documentation. AJCC manual Edition 8.

2: During the physical exam if the subject is experiencing visual changes, further investigation may be warranted with an ophthalmologic exam including at least the visual acuity and slit-lamp tests. This determination will be at the discretion of the site investigator. Vital signs to include temperature, pulse, respirations, blood pressure weight, and height (screening only) and ECOG performance status.

3: ECG will be performed at screening then Day 1 of each Cycle. An ECHO will be performed at screening to assess LVEF. Testing during and after study treatment is at the discretion of the site investigator.

4: A basic neurologic exam will be performed by the site investigator at screening, Day 1 of each Cycle of treatment and at the D30 safety follow up visit to monitor for neurologic toxicity. The Mini Mental Status Exam (MMSE) will be performed by a member of the research staff at screening and Day 1 of each Cycle of treatment to monitor for cognitive toxicity. The results of the MMSE and neurologic exam will be reviewed by the site investigator who will determine whether dose reduction of study drug(s) is required. This information should be retained.

5: CBC with differential and platelet to include: WBC, ANC, ALC, Hgb, PLT. Comprehensive metabolic profile (CMP) will be done at screening then Day 1 of each Cycle. During Cycle 1, a CMP should be performed at Cycle 1 Day 15. CMP to include glucose, calcium, BUN, creatinine, sodium, potassium, chloride, serum albumin, total bilirubin, alkaline phosphatase, AST, and ALT, ammonia, LDH and uric acid. Coagulation studies (PT/INR and PTT) will be done at screening then at the discretion of the treating investigator during treatment. For women of childbearing potential (WOCBP): urine or serum β hCG if clinically appropriate. If a urine test is done and it is positive or cannot be confirmed as negative, a serum pregnancy test will be required. Testing is required within 72 hours prior to initiation of study treatment. Urinalysis will be performed at screening.

6: Tumor response assessment will consist of evaluation by CT scans of chest and MRI or CT of abdomen and pelvis at screening and every odd numbered cycle starting after screening with CT scan before Cycle 3 (imaging selected for each subject should remain the same throughout the study); tumor imaging to be done at the safety follow up visit is at discretion of site investigator. If tumor assessments are available for subjects who have not yet experienced progressive disease (PD) at the time treatment is discontinued, the follow-up tumor evaluations will be documented in the eCRF until PD or death is confirmed, or until another treatment is initiated. MRI of the brain will be performed per standard of care for those subjects with a history of brain metastasis. A window of - 7 days may be used. CT/MRI images are to be submitted for central analysis. Images will be de-identified prior to sending to a central location. Central analysis to be performed upon receipt of funding.

7: Cycle = 28 days. PAC-1 will be taken once daily, Days 1-21. For Cycle 1, PAC-1 will be given on Day 1 and withheld on Days 2 and 3. The dose on these days is being held in order to determine the PK of single-agent entrectinib on Day 3 of the cycle. PAC-1 treatment will be re-

initiated on Day 4 and continue until Day 21 of the 28 day cycle. Administration of PAC-1 on Days 1 and 21 of Cycle 1 will occur in the morning. Entrectinib will be taken once daily, Days 1-28. Entrectinib therapy will be withheld on Days 1 and 2 and initiated during Cycle 1 on Day 3 to continue until Day 28 of the 28 day cycle. Administration of entrectinib on Days 3 and 21 of Cycle 1 will occur in the morning. Entrectinib administration will occur 1 hour before PAC-1 on Day 21.

8: The PK and PD analyses will occur with each dose level during Phase Ib. Pharmacokinetic and pharmacodynamic sample collections will occur in the mornings on Day 1(PAC-1 only), Day 3 (entrectinib only), and Day 21 (PAC-1 and entrectinib) of the first cycle. Day 1 Cycle 1: Subjects receive only PAC-1. Blood samples are collected immediately prior to oral ingestion of PAC-1 and at the following time points after ingestion: 0.5, 1, 2, 3, 4, 6, 7, and 24 hours. Day 3 Cycle 1: Subjects receive only entrectinib. Blood samples are collected immediately prior to oral ingestion of entrectinib and at the following time points after ingestion: 0.5, 1, 2, 3, 4, 6, 7, and 24 hours. Day 21 Cycle 1: Subjects receive both PAC-1 and entrectinib. Entrectinib will be taken 1 hour before PAC-1. Blood samples are collected immediately prior to oral ingestion of entrectinib, 0.5 hour before ingestion of PAC-1, and at the following time points after ingestion of PAC-1: 0.5, 1, 2, 3, 4, 6, 7, and 24 hours. See Correlative Laboratory Manual (CLM) for additional details regarding these samples.

9: Subject consent will be obtained for collection of peripheral blood samples prior to treatment on Cycle 1 Day 1, Cycle 2 Day 1 and at progression (safety visit). For subjects who come off treatment due to progression, the sample may be obtained during the safety visit. Specimens will be used for analysis of circulating tumor cells (CTCs), analysis related to mechanisms of action as well as ctDNA. Somatic baseline testing will be performed prior to treatment Cycle 1 Day 1. Blood that is leftover after initial protocol specific testing is performed will be stored for future correlative testing as described in Section 8. See CLM for additional details regarding these samples.

10: Archival tissue (metastatic disease preferred) is required if available and should be identified at screening and shipped prior to Cycle 1 Day 1. If archival tissue is not available, a biopsy is required prior to Cycle 1 Day 1 treatment (Cap of 15 biopsies). Tissue that is leftover after initial protocol specific testing is performed will be stored for future correlative testing as described in Section 8. See CLM for additional details regarding these samples.

11: If screening (baseline) CBC, CMP, magnesium, Lactate Dehydrogenase, uric acid and PT/PTT/INR were performed within 7 days of Cycle 1 Day 1 of treatment, these do not need to be repeated. All laboratory assessments should be done prior to treatment.

12: Safety Follow Up: The safety follow-up visit should only occur when subjects permanently stop study treatment for whatever reasons (toxicity, progression, or other reason) and should be performed 30 days (+ 7 days) after the last dose of treatment. Subjects with unresolved treatment-related toxicity should be followed as medically appropriate or until stabilization of toxicity.

13: Long Term Follow Up: Radiographic disease assessment should be performed at physician discretion. Subjects will be followed for survival every 2 months (+14 days) for 12 months from Cycle 1 Day 1 then every 3 months (+21 days) for up to 24 months. Follow up may be accomplished via clinic visit, phone call, or other avenues as appropriate.

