5.1.2 Definition of Dose-Limiting Toxicity

Toxicity and adverse events will be classified according to NCI's Common Terminology Criteria for Adverse Events Version 5.0 (CTCAE v.5).

Dose limiting toxicity (DLT) is defined as one of the following events **that are at least possibly related** to study medications occurring during Cycle 1 (first 28 days):

- Grade 3 or greater hematologic toxicity during the first cycle (28 days) of therapy.
- Cerebrovascular ischemia or cerebrovascular hemorrhage of any duration or grade.
- Grade 3 or greater clinical non-hematological toxicity (excluding \geq grade 3 nausea, vomiting, or diarrhea lasting less than < 72 hours with maximal medical intervention and/or prophylaxis) during the first cycle (28 days) of therapy.
- Delay of Cycle 2 treatment start by more than 2 weeks due to incomplete hematologic recovery ($ANC \geq 1.5 \times 10^9/L$ or platelets $\geq 100 \times 10^9/L$) or unresolved treatment related grade 3 or greater non-hematologic toxicity.
- Grade 2 or greater treatment related neurological toxicity occurring during the first cycle of therapy and lasting more than 72 hours.
- Hepatic labs meeting Hy's Law (concomitant elevations of AST/ALT and bilirubin of 3x ULN and 2xULN respectively without alternative etiology)

DLT's will be counted based on the number of patients with DLT at a given dose level, not the absolute number of DLTs. No single patient can trigger more than one DLT event. Additional patient cohorts will not be enrolled until all patients at the current dose level complete all planned treatment for Cycle 1 and are able to start Cycle 2 with no more than a 2-week delay.

Intra-subject dose escalation is not permitted. Once the MTD of PAC-1 in combination with entrectinib is determined, enrollment will continue until at least 6 subjects total are accrued at the maximum tolerated dose.

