8.1.1.2 Pharmacodynamic Assessment

The pharmacodynamic (PD) effects of PAC-1 (Days 1 and 21 of Cycle 1), and entrectinib (Days 3 and 21 of Cycle 1), may be used to assess the systemic responses of individuals following PAC-1 or entrectinib doses administered orally. Systemic variables are defined as plasma concentrations of PAC-1 or entrectinib, which will be measured and used to assess whether PAC-1 or entrectinib has affected the production of these biological markers. Measures of toxicity (e.g., changes in WBC counts, differential cell populations, platelets, etc.) are also considered systemic PD variables.

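### No blood count is scheduled between the first dose and Cycle 2 Day 1, so transient, asymptomatic Grade 3 or greater cytopenias that would be DLTs can be missed in Phase 1b

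*Combined protocol and SAP*

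**What the plan says.** **DLT definition (Section 5.1.2).** A DLT must be one of the listed Cycle 1 events "that are at least possibly related" to study medications. One of them is "Grade 3 or greater hematologic toxicity during the first cycle (28 days) of therapy". It carries no duration limit, although the same list sets 72-hour limits for nausea, vomiting and diarrhea and for neurological toxicity. A separate criterion covers a Cycle 2 delay of more than 2 weeks, including delay from incomplete hematologic recovery.

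**Blood counts (Section 7).** The CBC row is marked at screening, Cycle 1 Day 1, Day 1 of later cycles and the safety visit. Footnote 5 defines the count: "CBC with differential and platelet to include: WBC, ANC, ALC, Hgb, PLT". It gives the count no mid-cycle day. It does add one Cycle 1 draw: "During Cycle 1, a CMP should be performed at Cycle 1 Day 15". The contents of that panel are itemised: "CMP to include glucose, calcium, BUN, creatinine, sodium, potassium, chloride, serum albumin, total bilirubin, alkaline phosphatase, AST, and ALT, ammonia, LDH and uric acid". No blood count is among them. Footnote 11 says "All laboratory assessments should be done prior to treatment" and lets a screening CBC taken within 7 days stand in for Cycle 1 Day 1.

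**Dosing days (Section 7, footnote 7).** PAC-1 ends on Day 21 of each cycle. Entrectinib continues to Day 28.

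**MTD rule (Sections 2.4.1 and 5.1.1).** The MTD is the highest tested dose with a Cycle 1 DLT rate below 33%, stated as at most 1 of 6 subjects. There is no escalation beyond dose level 2.

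**The concern.** DLT is the event behind the Phase 1b primary endpoint. The definition counts a Grade 3 or greater fall in counts even if it is brief, but the calendar has no scheduled measurement that would show a brief fall. Missed events can only lower the observed DLT rate, so the error favours clearing a dose level. With a limit of 1 in 6, one missed event can change the decision.

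The dose chosen goes to 29 further subjects in Phase 2 (Section 12.3.1). After that, the only numerical stopping rule concerns treatment-related deaths (Section 12.2), alongside twice-yearly DSMB review (Section 13.1). The neutrophil and platelet thresholds in the PAC-1 modification table (Section 6.2) have the same weakness: in mid-cycle they depend on counts that nobody is scheduled to draw.

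**Working it through.** **1. Scheduled counts in the DLT window**

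| Time | CBC scheduled? | Source |
|---|---|---|
| Cycle 1 Day 1 | Yes, but before dosing, so a baseline value | Calendar; footnote 11 |
| Day 15 | No, CMP only | Footnote 5 |
| Day 21 | No, plasma PK/PD samples only (Phase 1b) | Calendar; footnote 8 |
| Cycle 2 Day 1 | Yes | Calendar |

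Scheduled CBCs after the first dose and before Cycle 2 Day 1: 0. Cycle 2 Day 1 is nominally Day 28 + 1 = Day 29, or Days 26 to 32 with the ±3-day window. It can therefore fall after the 28-day DLT period. The nominal gap after the last PAC-1 dose is Days 22 to 28, which is 7 days. The weekly repeats in Section 6.1 apply only when counts block the start of a new cycle.

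**2. The plan's own rule reproduces**

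1/6 = 16.7%, below 33%. 2/6 = 33.3%, above 33%. The rate limit and the count limit agree.

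**3. Direction and range of the bias**

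The documents give neither the true DLT rate, nor the hematologic share of DLTs, nor the share of those that would be missed. All three are assumptions:

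- p = true DLT rate. The main case is 0.40, because a dose must exceed the plan's 33% limit before accepting it is an error by the plan's own definition.
- h = share of DLTs that are hematologic only.
- m = share of those missed. The main case is 0.5.

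Observed rate: q = p × (1 − h × m).

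Once dose level 2 is opened, the 3+3 rule accepts it if at most 1 of 6 subjects has a DLT:

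P = (1 − q)^6 + 6q(1 − q)^5

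| Case (p = 0.40) | q | P(at most 1 of 6) |
|---|---|---|
| Full detection | 0.400 | 0.047 + 0.187 = 0.23 |
| h = 1/3, m = 1/2 | 0.40 × 5/6 = 0.333 | 0.088 + 0.263 = 0.35 |
| h = 1/2, m = 1/2 | 0.40 × 3/4 = 0.300 | 0.118 + 0.303 = 0.42 |
| h = 1, m = 1/2 | 0.40 × 1/2 = 0.200 | 0.262 + 0.393 = 0.66 |

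In the extreme case (h = 1, m = 1/2) at other true rates, P goes from 0.36 to 0.74 at p = 0.33, and from 0.11 to 0.53 at p = 0.50.

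Dose level 1 moves the same way. The chance of clearing it is (1 − q)^3 + 3q(1 − q)^5. At p = 0.40 this is 0.31 with full detection (q = 0.40), 0.49 at q = 0.30 and 0.71 at q = 0.20.

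**The case against.** **Much hematologic toxicity would still be found.** Counts are required before every new cycle and repeated weekly if low (Section 6.1). A cytopenia that persists to Cycle 2 Day 1 is seen, and one that delays Cycle 2 by more than 2 weeks is itself a DLT. Symptomatic events can prompt an unscheduled count. This stands, and it limits the gap to transient, asymptomatic events. A reader might infer that mid-cycle DLTs in general are found only by chance. The documents do not support that: the other DLT types do not depend on a CBC, and the Day 15 CMP covers the liver tests.

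**Recovery before Cycle 2 Day 1 is assumed.** This also stands. A reader might take Days 22 to 28 as drug-free, but only PAC-1 is off. Entrectinib continues, and Section 6.3 treats it as a possible cause of hematologic toxicity. The documents give no time course for counts.

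**Section 8.1.1.2 might seem to supply, or require, a count near Day 21.** It says "Measures of toxicity (e.g., changes in WBC counts, differential cell populations, platelets, etc.) are also considered systemic PD variables". But the pharmacodynamic assessment there is optional, Section 8 analyses depend on funding, and no CBC is scheduled. The text neither closes the gap nor creates a duty to draw one. Sample details are left to a laboratory manual that is not part of the documents.

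**The consequence is bounded.** Escalation stops at dose level 2, the sponsor-investigator may recommend a lower Phase 2 dose (Section 5.1.1), and safety is reviewed before Phase 2 (Section 5.2). These limit the harm. None of them recovers an event that was not measured.

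**Conclusion.** The concern holds for transient, asymptomatic cytopenias of Grade 3 or greater that are at least possibly related to study drug. The definition counts them, the calendar has no scheduled means of seeing them, and no other section fills the gap. The bias has one direction, toward clearing a dose level.

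Its size cannot be derived from the documents. At an assumed true DLT rate of 40%, acceptance of dose level 2 rises from 0.23 to 0.35 or 0.42 when one third or half of DLTs are hematologic and half of those are missed. The rise to 0.66 requires every DLT to be hematologic. These figures show direction and range and are not estimates. A reader might infer that the MTD will be set too high. The documents do not support that, because they give no rate of hematologic toxicity for the combination.

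**What to change.** Reconcile Section 5.1.2 with the Section 7 calendar and footnote 5. Add a CBC with differential to the Cycle 1 Day 15 draw already planned for the CMP and, in Phase 1b, to the existing Day 21 PK draw. The sponsor should also state whether a CBC was meant to accompany the Day 15 CMP.

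The cost is one or two extra tubes at draws that already take place, so this is a cheap improvement. It may also lead to more counted DLTs, which matters when 2 of 6 ends a level. Isolated lymphopenia is the likely point of friction: Section 5.1.2 does not exempt it, while the entrectinib table in Section 6.3 allows treatment to continue without interruption at Grade 3 or 4 if there are no other dose-limiting events. Those two sections should be reconciled before the extra counts begin.
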